- Exploring the impact of different levels of intervention receipt (adherence) and fidelity of intervention delivery on outcomes. We will use either two-stage least squares instrumental variables regression or inverse probability of treatment weighting methods to examine the effect of the intervention in those who receive varying levels of it.

All analyses will be checked subject to satisfying required assumptions. These checks include:

1. Linearity – plotting residuals vs predictor(s). If a structure is present, then transformation or an alternate model specification is required (i.e. GLM).
2. Homogeneity of variance – variance of the residuals across groups is the same. There is scope to fit models allowing for heterogeneous groups, but the setup is different (Generalized linear mixed model - GLMM).
3. Residuals are approximately normally distributed – plotting QQ plot

If distributional assumptions are not satisfied, as appropriate, a generalized linear model with alternate link function will be used. Alternatively, data transformation could be used but use of the GLM is preferable.

Longitudinal follow-ups (12 months post-randomisation)

We will fit linear mixed models, accounting for repeated post-randomisation measures (6- and 12-months post-randomisation) within participants, adjusting for baseline measures, adolescent factors (age, gender, parents in household), local authority and practitioners to investigate the overall effect of the intervention on post-randomisation measures.

Exploratory mediation analyses may also be carried out to examine variables at 6 months that may mediate intervention effects between baseline and 12-month follow-up. Any such analyses will be specified once a final Logic Model is confirmed. We would, however, anticipate

a theoretically derived set of questions relating to changes in parenting practices to mediate the impact of intervention on SDQ outcomes.

Analyses described in this section will be reported in the 12-month post-randomisation report only.

Withdrawal & participant retention

Withdrawal

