- Parenting scale Adolescent: Baseline, 6-month and 12 month follow up data will be collected. Baseline and 6-month follow up data will only be used in the main secondary analysis, but will be repeated in the 12 month followup addendum report. The PSA is a 30 item measure with each item scored on a 7 point scale. A total score is created by summing all items, with low scores indicating good parenting and high scores indicating dysfunctional parenting.
- Dyadic Adjustment Scale (DAS-7): Baseline, 6-month and 12 month follow up data will be collected. Baseline and 6-month follow up data will only be used in the main secondary analysis, but will be repeated in the 12 month followup addendum report. The DAS-7 is comprised of varying response scales, including both ordinal and Likert scales.
 - Items 1–3 use a 6-point ordinal scale (from 5 = ‘Always Agree’ to 0 = ‘Always Disagree’).
 - Items 4–6 also use a 6-point ordinal scale (from 0 = ‘Never’ to 5 = ‘More Often’).
 - Item 7 is rated on a 7-point Likert scale (from 0 = ‘Extremely Unhappy’ to 6 = ‘Perfect’)

The total score for the DAS-7 is the sum of the responses to the seven items. The resultant score ranges from 0 to 36, with a higher score indicating more positive relationship quality. Scores less than 21 are considered to indicate a relationship in distress.

- Parent mental health – the Kessler 6 (K6) : Baseline, 6-month and 12 month follow up data will be collected. Baseline and 6-month follow up data will only be used in the main secondary analysis, but will be repeated in the 12 month followup addendum report. The K6 is scored using a 5-level response scale, ranging from 0 to 4 (0 = none of the time, 1 = a little of the time, 2 = some of the time, 3 = most of the time, 4 = all of the time); this generates a scoring scale with a range of 0 to 24.
- Parent Wellbeing - The Warwick-Edinburgh Mental Well-being Scale (SWEMWBS) - short version: Baseline, 6-month and 12 month follow up data will be collected. Baseline and 6-month follow up data will only be used in the main secondary analysis, but will be repeated in the 12 month followup addendum report. The SWEMWBS is scored by first summing the scores for each of the seven items, which are scored from 1 to 5. The total raw scores are then transformed into metric scores using the SWEMWBS conversion table which can be found here: https://warwick.ac.uk/fac/sci/med/research/platform/wemwbs/using/howto/swemwbs_raw_score_to_metric_score_conversion_table.pdf

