Exploratory mediation analyses may also be carried out to examine variables at 6 months that may mediate intervention effects between baseline and 12-month follow-up. Mediation analyses will use the same two-level model setup as in the main analysis, but will have the following additional steps:

- Initial model, outcome regressed on all independent variables except mediator (same as main analysis).

$$Y_i = \beta_0 + \beta_1 SDQ_{BLi} + \beta_2 local_authority_i + \beta_3 TX_i + \varepsilon_i,$$

$$\varepsilon_i \sim N(0, \sigma^2)$$

- Second, the same model is fitted but the dependent measure is exchanged for the mediator.

$$M_i = \beta_0 + \beta_1 SDQ_{BLi} + \beta_2 local_authority_i + \beta_3 TX_i + \varepsilon_i,$$

$$\varepsilon_i \sim N(0, \sigma^2)$$

- Finally, the first model is refitted but with the inclusion of the mediator as an additional independent variable.

$$Y_i = \beta_0 + \beta_1 SDQ_{BLi} + \beta_2 local_authority_i + \beta_3 TX_i + \beta_4 M_i + \varepsilon_i,$$

$$\varepsilon_i \sim N(0, \sigma^2)$$

Using these model parameter estimates and the 'mediate' function from the R package 'mediation', the average causal mediation effects can be estimated following the procedure from Imai et al. (2010). The mediation analyses will use the bootstrapped procedure as this method has no distributional assumptions on the indirect effect and is generally more robust (Bollen & Stine, 1990).

Harms

The number (and percentage) of patients experiencing each AE/SAE will be presented for each treatment arm categorised by severity. For each patient, only the maximum severity experienced of each type of AE will be displayed. The number (and percentage) of occurrences of each AE/SAE will also be presented for each treatment arm. No formal statistical testing will be undertaken.

Statistical software

All statistical analyses will use R version 4.1.2 (2021-11-01) with additional packages: tidyverse, pwr, VGAM, lme4, lmerTest, performance, mice, psych, ivreg, and ivpack.

References

Joshua D. Angrist & Guido W. Imbens (1995) Two-Stage Least Squares Estimation of Average Causal Effects in Models with Variable Treatment Intensity, *Journal of the American Statistical Association*, 90:430, 431-442, 10.1080/01621459.1995.10476535

Barnett, A.G., & Dobson, A.J. (2008). *An Introduction to Generalized Linear Models* (3rd ed.). Chapman and Hall/CRC. <https://doi.org/10.1201/9781315182780>

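### The SAP's exploratory mediation models omit the mediator's own baseline, so the indirect effect can be inflated if the programme shifts parenting and baseline parenting also predicts 12-month SDQ

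*SAP*

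**What the plan says.** The SAP section on mediation (12-month report only) presents the analysis as optional: "Exploratory mediation analyses may also be carried out to examine variables at 6 months that may mediate intervention effects". It then gives three equations. The first regresses the outcome on baseline SDQ, local authority and arm. For the next step, "Second, the same model is fitted but the dependent measure is exchanged for the mediator". For the last, "Finally, the first model is refitted but with the inclusion of the mediator as an additional independent variable". The mediator's baseline score appears in none of them.

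On inference, "The mediation analyses will use the bootstrapped procedure as this method has no distributional assumptions on the indirect effect". The section gives no resampling unit, no decision rule for the indirect effect and no sensitivity analysis for mediator-outcome confounding. The SAP's general section on confidence levels makes all intervals 95% and two-sided.

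The SAP names no mediator. The protocol, under longitudinal follow-ups, anticipates "a theoretically derived set of questions relating to changes in parenting practices to mediate the impact of intervention on SDQ outcomes". The baseline score needed is available. In the SAP's section on the derivation of secondary outcomes: "Parenting scale Adolescent: Baseline, 6-month and 12 month follow up data will be collected".

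**The concern.** Arm is randomised, so its effect on the 6-month mediator is estimated without confounding. The mediator itself is not randomised. Its coefficient in the final outcome model has a causal reading only if the common causes of mediator and outcome are adjusted for. Baseline parenting is an obvious measured candidate: it is likely to predict 6-month parenting, it may predict 12-month behaviour, and the same parent rates both. Adjusting for baseline SDQ removes only the part of that association that baseline SDQ captures.

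The models also use the 6-month level of the mediator, whereas the protocol's hypothesis concerns change. With the baseline score in the outcome model the two agree, because the coefficient on the 6-month score is then the same as the coefficient on the change score. Without it, long-standing differences between families can pass for mediation. At stake is a mechanism claim that could be too large or, under some conditions, spurious.

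The SAP's covariate-adjustment paragraph does not close the gap. It considers extra covariates where large baseline imbalances are seen, and a confounder of the mediator-outcome path can be perfectly balanced between arms.

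**Working it through.** **Inputs from the documents.** 275 families, 1.5 parents per family, 20% of families lost by 12 months, family ICC 0.5, baseline-to-follow-up correlation 0.5 for SDQ (the sample size sections of both documents). Analysed set: 275 × 0.8 = 220 families; 220 × 1.5 = 330 parents.

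**Assumptions not in the documents.** Baseline parenting–SDQ correlation 0.3; mediator stability s = 0.5 to 0.7; programme shift in the mediator a = 0 to −0.5 SD; effect of baseline parenting on 12-month SDQ beyond baseline SDQ c = 0 to 0.3 SD per SD; direct effect −0.2 SD; ICC 0.5 carried over to the mediator.

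**Step 1: the plan's own figure.** The plan gives no figure for mediation. Its sample size is reproduced closely: 172 per arm (d = 0.35, 90% power, two-sided 5%) × [1 + 0.5 × 0.5] × [1 − 0.5²] ÷ 0.8 = 172 × 1.25 × 0.75 ÷ 0.8 = 201.6, so 202 per arm and 404 in total (406 from the t-test version), against 412 stated. Power at 412 is 0.907.

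**Step 2: the bias in closed form.** Let M6 = s·M0 + a·T + error and Y12 = 0.5·S0 + c·M0 + b·M6 − 0.2·T + error, where M0 is baseline parenting, S0 baseline SDQ and T arm. With M0 left out, the coefficient on M6 tends to b + c·k, where k = s(1 − 0.3²) ÷ (1 − 0.3²·s²).
- s = 0.5: 0.455 ÷ 0.9775 = 0.465
- s = 0.6: 0.546 ÷ 0.9676 = 0.564
- s = 0.7: 0.637 ÷ 0.9559 = 0.666

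The indirect effect is therefore off by a·c·k, which is zero if a = 0 or c = 0.

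**Step 3: simulation with no true mediation (b = 0).** 600 trials per row, 300 bootstrap draws, families resampled, local-authority terms included.

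| a | s | c | a·c·k | mean simulated indirect effect | interval excludes 0, SAP models | same, M0 added to both models |
|---|---|---|---|---|---|---|
| −0.35 | 0.6 | 0.1 | −0.0197 | −0.0196 | 15.2% | 5.5% |
| −0.35 | 0.6 | 0.2 | −0.0395 | −0.0392 | 46.8% | 4.3% |
| −0.35 | 0.6 | 0.3 | −0.0592 | −0.0589 | 69.2% | 4.2% |
| −0.5 | 0.5 | 0.2 | −0.0465 | −0.0456 | 43.5% | 6.0% |
| −0.5 | 0.7 | 0.2 | −0.0666 | −0.0673 | 75.0% | 5.5% |
| −0.5 | 0.7 | 0.3 | −0.1000 | −0.0982 | 94.7% | 4.2% |

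Repeat simulations gave about 12% at a 0.35 SD shift, c = 0.1, s = 0.5; about 18% and 40% at a 0.35 SD shift, s = 0.6, c = 0.1 and 0.2; and about 70% at a 0.5 SD shift, s = 0.7, c = 0.2. With M0 added, the rates were 2% to 7%. Monte Carlo error with 600 trials is √(0.05 × 0.95 ÷ 600) = 0.9 points near 5% and √(0.5 × 0.5 ÷ 600) = 2.0 points near 50%.

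**Step 4: when a condition is missing or weak (SAP models, family resampling).**
- a = 0: 3.3% (c = 0.2, s = 0.6) and 4.5% (c = 0.3, s = 0.7).
- a = −0.35, c = 0: 5.2%.
- Shift 0.2 SD with c = 0.1, or 0.35 SD with c = 0.05 (s = 0.5): 5% each.

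**Step 5: when mediation is real.** With a = −0.35, b = 0.2, s = 0.6, the true indirect effect is −0.35 × 0.2 = −0.070. At c = 0.2 the SAP models should give −0.35 × (0.2 + 0.2 × 0.564) = −0.109, and the simulation gave −0.1087. As −0.1087 ÷ −0.070 = 1.55, this is about 55% too large. With M0 added it was −0.0675.

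**Step 6: resampling unit and precision.** Resampling parents instead of families gave 9.3% against 4.5% at a = 0, c = 0.3, s = 0.7. At a = −0.35, c = 0.2, s = 0.6 it gave 52.5% against 46.8%, and 7.2% against 4.3% with M0 added. Putting M0 in the mediator model raised power for the arm-to-mediator path from about 0.80 to 0.93 (a = −0.35, s = 0.6).

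**The case against.** The analysis is exploratory, optional and confined to the 12-month report. The protocol defers its specification until the logic model is final, the SAP names no mediator, and no decision rule is attached to the indirect effect. The documents give no value for a, c or s. The 0.5 correlation and the 0.5 ICC are stated for SDQ, not for the Parenting Scale. All of this stands. It limits the importance of the point and makes the size a range.

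A reader might infer that the bootstrap test rejects because of pre-trial parenting differences, or that any movement in parenting will yield a significant indirect effect. The documents do not support either. Allocation is randomised, so pre-trial differences do not bias the arm-to-mediator path, and Step 4 shows no inflation when a or c is zero or small. The direction also depends on the assumed sign of c (worse baseline parenting, more later problems). When mediation is real, rejection is largely genuine and the fault is in the size of the estimate.

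A reader might also infer that clustering is ignored, because the printed mediation equations have no family random intercept. The text of that section says that the two-level structure of the main analysis applies, and the SAP prints the same single-level form for its fallback primary model while specifying cluster-robust standard errors. What can be said is that the bootstrap unit is not stated.

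The objection does not remove the omission itself. The first condition is what the trial hopes for, since improved parenting practices are a secondary objective. The second is plausible though unproven: a correlation of 0.5 leaves 1 − 0.5² = 75% of follow-up SDQ variance unexplained by baseline SDQ.

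**Conclusion.** The concern holds in conditional form. The mediation models omit a measured pre-randomisation variable that can confound the mediator-outcome path. If the programme shifts the mediator and baseline parenting predicts 12-month SDQ beyond baseline SDQ, the indirect effect can be inflated and its 95% interval can exclude zero with no true mediation. Over the assumed ranges (shift 0.35 to 0.5 SD, stability 0.5 to 0.7, association 0.1 to 0.3 SD per SD) this occurs in roughly 12% to 95% of trials with family resampling, against about 2% to 7% after the change. In the one scenario examined with both real mediation and confounding, the estimate was about 55% too large.

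The return to about 5% assumes that baseline parenting is the only omitted confounder and is measured without error, so the change should not be read as removing all bias. Only the optional exploratory mediation analysis is affected.

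**What to change.** In the SAP's mediation section:
- Add the mediator's baseline score to the mediator model and to the final outcome model, keeping baseline SDQ, local authority and arm. The outcome-model term removes this source of bias; the mediator-model term adds precision.
- State that the bootstrap resamples whole families, in keeping with the two-level structure that the section already adopts.
- Describe the result as mediation by the 6-month mediator conditional on its baseline, and say that other mediator-outcome confounding may remain. A short sensitivity analysis for it would be a sensible addition.

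The cost is SAP wording, one covariate in two equations and a stated resampling unit. The Parenting Scale is already collected at baseline, so no new data are needed.

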Appendix A

CONSORT 2010 Flow Diagram for Cluster RCT

youthendowmentfund.org.uk

[contact]

[@YouthEndowFund](https://twitter.com/YouthEndowFund)

The Youth Endowment Fund Charitable Trust

Registered Charity Number: 1185413
